11.2 Medical History

The medical history will be coded with the most recent Medical Dictionary for Regulatory Activities (MedDRA®) version, Version 20.1 or later.

Medical history will be listed by subject, based on the safety population, and will include the following information:

- Description of medical condition
- System Organ Class (SOC)
- MedDRA Preferred Term (PT)
- Start/End Date (or ongoing, if applicable)
- Toxicity grade (if applicable)
- Relation to study condition

11.3 Disease History and Prior Anti-Cancer Therapies

The safety population will be used for all disease history and prior anti-cancer therapy related outputs.

Disease history will be listed including the following information:

- Site of primary tumor
- Sub Sites
- Date of initial cancer diagnosis
- Date of documented locally advanced, inoperable or metastatic disease (if applicable)
- Histopathological classification
- T, N and M classification at initial diagnosis
- T, N and M classification at study entry

The disease history will be summarized by dose group and overall using the safety population for the following categorical variables:

- T, N and M stages at study entry
- Time since initial diagnosis (months)
- Time since documentation of locally advanced, inoperable or metastatic disease (months)
- Histopathological classification

Incomplete dates for disease history (initial diagnosis date, date of documented locally advanced, inoperable or metastatic disease) will be imputed as follows:

- If the day is missing, it will be imputed to the 15th day of the month.
- If both day and month are missing and the year is prior to the year of the first study treatment, the month and day will be imputed as July 1st.
- If both day and month are missing and the year is same as the year of the first study treatment, the month and day will be imputed as January 1st.
- If the date is completely missing, no imputation will be performed.

Prior anti-cancer drug therapy will be listed including the following information:

- Regimen number
- Intent and type of therapy
- Reason for discontinuation

- Best response
- Date of documented progression disease (if applicable)
- For each drug given as part of the regimen:
 - o Name of drug (coding as described in Section 12)
 - Start and end date

Prior anti-cancer radiotherapy will be listed including the information:

- Regimen number
- Location
- Start and end dates
- Total dose
- Number of fractions

Prior anti-cancer surgeries will be listed including the following information:

- Name of surgery
- Date of surgery
- Intent of surgery
- Outcome of surgery

A summary of prior anti-cancer therapies will be added to the disease history, displaying number of surgeries, radiotherapy regimes and anti-cancer drug regimes.

12 Previous or Concomitant Medications/Procedures

The safety population will be used to list and summarize previous and concomitant medications.

Concomitant treatments are medications, other than trial medications, which are taken by subjects any time on-trial (on or after the first day of trial drug treatment for each subject) or within 28 days after last dose of trial drug. In case the date values will not allow to unequivocally allocate a medication to concomitant medication, the medication will be considered as concomitant medication.

Previous medications are medications, other than trial medications and pre-medications for trial drug, which started before first administration of trial drug. In case the date values will not allow to unequivocally allocate a medication to previous medication, the medication will be considered as previous medication.

All medication will be coded with the most current World Health Organization – Drug Dictionary (WHO-DD) version September 2017 or later.

Both previous and concomitant medication will be listed including the following information:

- Name of medication
- Anatomical Therapeutic Chemical (ATC) 2nd level and Preferred Term (PT)
- Start and end date
- Dose and frequency
- Route of administration
- Reason for medication

All concomitant medication will be summarized by dose group and overall, ATC 2^{nd} level and PT.

In case multiple ATC's are assigned to a drug, all ATC 2nd level will be used for reporting.

All **concomitant procedures**, which were undertaken any time on trial, will be listed, showing the following information:

- Name of procedure
- Start and end date
- Reason for procedure

13 Treatment Compliance and Exposure

Exposure to the IMP will be listed using the safety population, showing the following information:

- Cycle and day in cycle
- Date and time of administration
- Actual dose
- Whether dose has been adjusted, and if yes, reason why
- Reason for no dose (if applicable)

Using the safety population, compliance and exposure will be summarized by dose group and overall, including duration of therapy (weeks), number of times dose missed (overall and by reason) and number of times dose was adjusted (overall and by reason).

14 Efficacy Analyses

14.1 Analysis of Best Overall Response, Clinical Benefit and Progression-free Survival Time

All efficacy endpoints will be listed and summarized descriptively as described in Section 9.2. The following categorical variables will be included:

- Best overall response (BOR: complete response [CR], partial response [PR], stable disease [SD] or progressive disease [PD] according to RECIST v 1.1; objective response rate [ORR=CR+PR].)
- Clinical benefit (CR, PR and SD for ≥ 12 weeks: yes/no)

In addition, 95% exact Clopper Pearson Confidence intervals will be calculated for the overall clinical benefit rate and the ORR (regardless of dose level).

Furthermore, the following variable will be analyzed:

• Progression-free survival time (PFS)

PFS time is defined as the time from start of treatment to the date of the first documentation of objective progression of disease (PD) or death due to any cause, whichever occurs first. PFS data will be censored on the date of the last adequate tumor assessment for patients who do not have an event (PD or death) at data cutoff, or for patients with an event after two or more subsequent missing response assessments (i.e. 2 times the scheduled time interval between two subsequent response assessments, plus 1 week time window). Patients who do not have a baseline tumor assessment or who do not have any post-baseline tumor assessments will be censored at start of treatment unless death occurred on or before the time of the second planned tumor assessment in which case the death will be considered an event.

The date of the overall response assessment is the earliest date of imaging of target, non-target and new lesions of images taken at that response assessment.

	Status	Censoring	Date of event / censoring
Progressed or died	Within two subsequent scheduled tumor assessments after last response assessment of CR, PR or SD or treatment start	Event	Minimum(Date of PD, Date of death)
	Otherwise	Censored	Date of last tumor assessment with outcome CR, PR or SD or date of treatment start, whatever is later
Neither progressed n	or died	Censored	Date of last tumor assessment with outcome CR, PR or SD or date of treatment start, whatever is later

The censored values will be presented descriptively. Number of and reason (PD/Death after two or more subsequent missing response assessments, censored at treatment start, lost to follow-up / withdrew consent, due to data cutoff (administrative censoring)) for censored values will be displayed, including percentages.

In the listing censored values will be flagged and the reason for censoring will be displayed.

Kaplan-Meier estimates (product-limit estimates) will be presented for the analysis of PFS together with a summary of associated statistics (median survival time, 6-, 12-, 18-, 24-month survival rate estimates and estimates for every 6 months thereafter if applicable) including the corresponding two-sided 95% confidence intervals, presented overall, and for daily dose \leq /> median daily dose.

The confidence intervals for the median will be calculated according to Brookmeyer and Crowley (1982) and confidence intervals for the survival function estimates at above defined time points will be derived using the log-log transformation according to Kalbfleisch and Prentice (1980). The estimate of the standard error will be computed using Greenwood's formula.

The safety population will be used for the analysis of efficacy.

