5.3.1 Inclusion Criteria

5.3.1.1 Part 1, M8891 Single Agent, Solid Tumors

Subjects are eligible to be included in the study only if all the following criteria apply:

1. Subjects must be refractory to or intolerant of existing cancer therapy(ies) known to provide clinical benefit.
2. Histologically confirmed advanced solid tumors with no clear curative treatment options available after at least 1 prior systemic anticancer therapy
3. Male and female subjects age 18 years and older who are able and willing to give written informed consent
4. A male subject must agree to use and to have their female partners to use a highly effective contraception (i.e., methods with a failure rate of less than 1% per year) as detailed in [Appendix I](#) of this protocol before first dose of study treatment (as appropriate), during the treatment period and for at least 92 days (3 months) after the last dose of study treatment and refrain from donating sperm during this period.
5. A female subject is eligible to participate if she is not pregnant (see [Appendix I](#)), not breastfeeding, and at least one of the following conditions applies:
 - a. Not a woman of childbearing potential (WOCBP) as defined in [Appendix I](#)
 - b. A WOCBP who agrees to use a highly effective contraception (i.e., methods with a failure rate of less than 1% per year) as detailed in [Appendix I](#) of this protocol before start of first dose of study treatment (as appropriate), during the treatment period and for at least 92 days (3 months) after the last dose of study treatment.
6. Tumor accessible for biopsies and agreement to conduct pre-dose and post-dose fresh tumor biopsies. Archival tumor tissue is not mandatory for the inclusion in the study but is strongly recommended.

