5.3.1.2 Part 2, M8891 combined with Cabozantinib, mRCC

Subjects are eligible to be included in the Part 2 of the study only if all the following criteria apply:

1. Male and female subjects age 18 years and older who are able and willing to give written informed consent before the performance of any study-specific procedures.
2. Eastern Cooperative Oncology Group Performance Status (ECOG PS) of 0 to 1 at Screening.
3. Histologic or cytologic evidence/proven of mRCC with clear cell component.
4. Previous treatments:
 - a. **Part 2A:** Subjects should have progressed to 1 or more previous lines of systemic anticancer therapy, excluding treatment with cabozantinib.
 - b. **Part 2B:** Subjects should have progressed to 1 or 2 previous lines of systemic anticancer therapy, excluding treatment with cabozantinib. Subjects should have failed to only 1 previous TKI for metastatic disease. Adjuvant therapy with sunitinib will be considered as 1 line of therapy for metastatic disease in the case that disease progression occurs during or within 3 months of the completion of the treatment.
5. At least 1 lesion that is measurable using RECIST v1.1.
6. Ability to swallow capsules and tablets.
7. Recovery from any acute toxicities from the previous therapy to Grade 1.
8. Predicted life expectancy of > 3 months (according to the opinion of the Investigator).
9. Adequate organ function (i.e. liver, kidney, bone marrow), as evidenced by multiple laboratory value results within specific parameters. Specifically:
 - Hemoglobin \geq 9.0 g/dL (no transfusion in the past 2 weeks before first dose); neutrophil count $>$ 1.5 \times 10⁹/L; platelets $>$ 100 \times 10⁹/L (no transfusion in the past 2 weeks before first dose).
 - Glomerular filtration rate \geq 30 mL/min (according to the Cockcroft-Gault formula)
 - Total bilirubin \leq 1.5 \times ULN, AST/ALT \leq 2.5 \times ULN. For documented Gilbert's syndrome a total bilirubin $<$ 3 \times ULN is accepted.
10. Patients with central nervous system (CNS) metastases must have received surgical and/or radiation treatment and be neurologically stable no evidence of CNS disease progression as determined by CT or MRI within 21 days prior to the first dose of study drug.
11. Subjects on bisphosphonates may continue receiving bisphosphonates therapy during study treatment.

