6.5.1 Permitted Medicines

Any medications that are considered necessary to protect subject welfare and will not interfere with the trial medication may be given at the Investigator's discretion, e.g. hormone therapy is allowed for subjects with prostate cancer.

Rescue medications may be administered to address ineffective treatment, anticipated adverse reactions or anticipated emergency situations.

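### Part 1 admits subjects without measurable disease, but SAP 14.1 has no category for their stable disease, and its PFS table and text disagree on how to censor them

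*SAP*

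**What the plan says.** **Eligibility.** Part 1 (Protocol 5.3.1.1) asks for "Histologically confirmed advanced solid tumors with no clear curative treatment options available after at least 1 prior systemic anticancer therapy" and for "Tumor accessible for biopsies and agreement to conduct pre-dose and post-dose fresh tumor biopsies". Neither these criteria nor the exclusions in 5.3.2.1 mention measurability, and the deviation list in SAP 18.1 has no such item. Part 2 (Protocol 5.3.1.2) does require it: "At least 1 lesion that is measurable using RECIST v1.1".

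**Response.** SAP 14.1 lists best overall response as CR, PR, "stable disease [SD] or progressive disease [PD] according to RECIST v 1.1; objective response rate [ORR=CR+PR". Clinical benefit is "Clinical benefit (CR, PR and SD for ≥ 12 weeks: yes/no". Protocol 8.3.1.2 uses the same categories. Efficacy is analysed in the safety population, and SAP 9.2 keeps missing observations in the denominator.

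**PFS table (SAP 14.1).** Progression or death is an event if it occurs "Within two subsequent scheduled tumor assessments after last response assessment of CR, PR or SD or treatment start". All other subjects are censored at "Date of last tumor assessment with outcome CR, PR or SD or date of treatment start, whatever is later".

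**PFS text (SAP 14.1, above the table).** Subjects without an event are censored at the last adequate assessment, with no condition on its outcome. Adequate is not defined. An event is censored only after two or more consecutive missed assessments. Censoring at treatment start is kept for subjects with no baseline scan or no post-baseline scan, apart from an exception for early death.

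**The concern.** The protocol allows a subject to enter Part 1 with only non-target lesions, but the SAP does not say how that subject's stable disease is classified. Part 1 text leaves room for such subjects: the slow-progression rule in Protocol 5.1.3.1 mentions bone lesions, and Protocol 6.5.1 notes that "hormone therapy is allowed for subjects with prostate cancer".

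If the scans of such a subject are not labelled SD, the PFS table treats them as if they had never been done. Early progression would still count as an event, while lasting stability would leave the analysis on the first day. That is informative censoring, and it would pull the PFS curve down. Under clinical benefit the same subject would be a non-benefit or missing, yet still counted in the denominator. Antitumor activity is a stated secondary objective of Part 1.

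**Working it through.** The plan states no figure that depends on this rule, so there is nothing to reproduce. The check applies both rules to one type of subject.

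**Inputs**
- Scans on Day 1 of Cycles 3, 5 and 7, then every 18 weeks (Protocol Table 1 and 7.3). With 21-day cycles these fall on days 43, 85, 127 and 253, that is weeks 6, 12, 18 and 36.
- Window for a late event (SAP 14.1): 2 × scheduled interval + 1 week = 2 × 42 + 7 = 91 days, or 13 weeks.
- Duration = stop date − start date + 1 day; 1 month = 30.4375 days (SAP 9).
- Part 1 size: about 36 evaluable subjects, at most 42 (Protocol 8.1.1).

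**Assumption.** The subject has only non-target lesions, and the non-progressing scans carry a label other than CR, PR or SD. RECIST v1.1 is named in the documents, but its non-target-only categories are not reproduced there.

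**PFS under each rule, no scan missed**

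| Course | SAP table | SAP text |
|---|---|---|
| First PD on day 43 (42 days from start, ≤ 91) | event | event |
| First PD on day 85 (84 days, ≤ 91) | event | event |
| First PD on day 127 (126 days, > 91) | censored, 1 day | event |
| First PD on day 253 (252 days, > 91) | censored, 1 day | event |
| No event, last scan day 43 | censored, 1 day | censored, 43/30.4375 = 1.41 months |
| No event, last scan day 85 | censored, 1 day | censored, 2.79 months |
| No event, last scan day 127 | censored, 1 day | censored, 4.17 months |
| No event, last scan day 253 | censored, 1 day | censored, 8.31 months |

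**Direction.** Take four hypothetical subjects of this type: PD at week 6, PD at week 12, PD at week 18, and one event-free to week 36.
- Text rule: the Kaplan-Meier estimate is 3/4 = 75% after week 6, 75% × 2/3 = 50% after week 12, and 50% × 1/2 = 25% after week 18.
- Table rule: the last two leave on day 1. The estimate is 1/2 = 50% after week 6 and 0% after week 12.

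**Clinical benefit.** One subject not counted costs 1/36 = 2.8 points, or 1/42 = 2.4 points. The table below is an illustration only. It assumes n = 36 and 11 true benefits; neither the 11 nor the numbers lost are in the documents. Intervals are exact Clopper-Pearson 95%.

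| Stable non-target-only subjects not counted | Rate | 95% CI |
|---|---|---|
| 0 | 11/36 = 30.6% | 16.3–48.1% |
| 1 | 10/36 = 27.8% | 14.2–45.2% |
| 2 | 9/36 = 25.0% | 12.1–42.2% |
| 4 | 7/36 = 19.4% | 8.2–36.0% |
| 7 | 4/36 = 11.1% | 3.1–26.1% |

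**The case against.** The strongest reply is that the documents are coherent when read alone. Protocol and SAP use four categories throughout. If every evaluable scan without progression is CR, PR or SD, the table is just a working form of the text, and the two agree. A further category comes from the response standard, which the documents only name. This stands: the effect is conditional on how investigators record stable non-target-only disease. It does not remove the gap, because the SAP gives no rule, so classification would depend on site habit.

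Second, the text gives the sensible PFS result. The listed censoring reasons support it, since none describes progression after a complete set of scans. They do include censoring at treatment start as a reason, which could absorb these subjects, and nothing says whether text or table governs. The text also gives no help for best overall response or clinical benefit.

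Third, the evidence that such subjects exist is thin. A biopsy-accessible tumor is required, Protocol 7.3 expects target lesions to be selected, and SAP 14.2 plans change in target-lesion sums and spider plots. Prostate cancer appears only as a medication example, and bone lesions only in a rule for continuing treatment. This stands as a limit on size. A biopsy-accessible lesion need not be measurable.

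Fourth, these are secondary endpoints in a trial where all analyses are descriptive. That also stands.

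**Conclusion.** The gap is real and worth correcting. Part 1 does not exclude non-measurable disease, SAP 14.1 has no category for its stable form, and the PFS table and text of that section give different results for any adequate non-progressing scan without a CR, PR or SD label. If such labels occur, the table censors at treatment start subjects who never progress and subjects whose progression is first seen at week 18 or later, and neither group can count as clinical benefit on stability.

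A reader might infer more: that the plan firmly removes all stable non-measurable subjects from PFS on day 1, and that Part 1 activity is therefore understated by a calculable amount. The documents do not support that. The text of SAP 14.1 prescribes the opposite for PFS, progression or death within about 13 weeks of start is an event under both rules, and the share of subjects without measurable disease is not given. Any overall bias figure would be an assumed share multiplied by an assumed rate. An 18-week PFS comparison would also not match a planned statistic, since SAP 14.1 reports the median and 6-monthly rates.

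What can be said is the direction (downward, if the table governs) and the unit: about 2.8 points of clinical benefit per affected subject in 36. DLT and MTD analyses are unaffected.

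**What to change.** In SAP 14.1:
1. In every row of the PFS table, replace the outcome condition with the last adequate assessment not showing PD (CR, PR, SD or non-CR/non-PD), so that table and text agree. Define adequate.
2. Add non-CR/non-PD as a best overall response category for subjects with only non-target lesions.
3. Count non-CR/non-PD lasting at least 12 weeks as clinical benefit.

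Because clinical benefit and its categories are protocol endpoints, clarify the Protocol Synopsis and 8.3.1.2 to match. Reporting ORR also among subjects with measurable disease at baseline is optional.

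The cost is wording and programming, plus the protocol clarification. No new data are needed: SAP 14.2 already lists target, non-target, new-lesion and overall response at each assessment.

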14.2 Analysis of Response Evaluation Criteria in Solid Tumors (RECIST)

The results of the RECIST evaluation will be listed using the safety population and will contain the following information:

- Designation of lesion (target/non-target/new)
- Lesion number
- Site
- Assessment Method
- Imaging Date
- Type of lesion (primary, node or metastasis)
- Size (longest diameter for non-nodal, short axis for nodal)
- Sum of longest diameters of target lesions (mm, per assessment)
- PET result

The list will be sorted by dose group, subject, designation, number of lesion and date.

Overall disease assessment based on imaging (RECIST 1.1) will be listed, including the following information:

- Date of overall response assessment (as defined in Section 14.1)
- Time from start of treatment (months)

- Response target lesions
- Response non-target lesions
- New lesions
- Overall response

The percent change from baseline in sum of longest diameters (mm) for target lesions will be summarized by dose group and overall, and by time point.

Spider plots per dose group and overall will be produced. For each subject a different combination of color and line type will be used; all subjects in the same dose group will be presented using the same color.

14.3 Eastern Cooperative Oncology Group Performance Status (ECOG PS)

The ECOG PS assessments will be listed using the safety population, including date of assessment and performance status.

The shift from baseline to best and worst on-treatment ECOG PS, respectively, will be summarized by dose group based on the safety population. The missing category will be included and the number of subjects in each cohort will be used as the denominator. Also, the number of subjects with increase, decrease, as well as no change in ECOG PS compared to baseline during treatment, respectively, will be summarized.

15 Safety Analyses

15.1 Analyses of Dose Limiting Toxicities (Primary Endpoint)

The dose escalation set will be used for all analyses related to the primary endpoint. The frequency and percentage of subjects experiencing a dose limiting toxicity (DLT) will be summarized by dose group and overall. A listing will be provided as well (details on presented information, see Section 15.2).

In addition, the following will be presented:

• Quantiles (2.5%, 25%, 50%, 75% and 97.5%) for the posterior probability of a subject experiencing a DLT at each of the dose levels used in the study according to the same Bayesian Logistic Model (BLM) as descripted in the SMC IAP, Section 14:

Bayesian two-parameter logistic model:

Prior distribution and likelihood are used to calculate the posterior probabilities based on Bayes theorem.

The likelihood is defined based on a binomial distribution, modelling the rate of subjects with at least 1 DLT.

The prior distribution is set-up as follows:

The relationship between dose and toxicity rate is defined by

$$P(DLT|d_j, \alpha, \beta) = \frac{\exp\left(\alpha + \exp(\beta) * \log\left(\frac{d_j}{d_{ref}}\right)\right)}{1 + \exp\left(\alpha + \exp(\beta) * \log\left(\frac{d_j}{d_{ref}}\right)\right)}$$

Where suggested $d_j \in \{7 \text{ mg}, 12 \text{ mg}, 20 \text{ mg}, 35 \text{ mg}, 60 \text{ mg}, 100 \text{ mg}, 150 \text{ mg}, 210 \text{ mg}\}$ for QD (and (α, β))aere bivariate normally distributed.

the following is be derived:

$$E(\alpha) = \log(0.8/0.2) = 1.386$$

$$E(\beta) = \log((\log(0.33/0.67) - \log(0.8/0.2)) / \log(210/340)) = 1.469$$

Variances are chosen as follows: $Var(\alpha)=2^2$, $Var(\beta)=2^2$, $Cov(\alpha, \beta)=0.2$.

MTD suggestion from the BL model

The MTD as suggested from the modeling will be derived as follows:

- 1) The BLM will be updated with all DLT data from the dose escalation.
- 2) Estimated $E(\alpha)$, $E(\beta)$, $Var(\alpha)$, $Var(\beta)$ and $Cov(\alpha, \beta)$ as well as the estimated curve will be provided.
- 3) The dose with targeted toxicity probability of 30% will be identified using the curve.
- 4) The next lower tested dose will be selected.
- 5) It will be checked whether this dose fulfills the overdose control.

The credibility interval will be provided.

This information will be forwarded to the SMC that will decide on the determination of the MTD. Additionally, the SMC will receive the estimated DLT probability and associated probability quantiles for all other doses tested.

As second approach, the MTD as suggested by the frequentist estimation will also be derived:

 All DLT data from the dose escalation will be included in a two-parameter logistic regression model (intercept and slop over log of the scaled dose, no prior; if the model does not converge, it will be reported as not calculable; the program code for this analysis can be found in the TLF shells).

- 2) Steps 3) and 4) of the first approach will be followed.
- 3) The confidence interval for the DLT probability will be provided.

There will also be a plot showing both the observed percentage of DLTs and the 75% quantile for the predicted probability according to the BLM over dose. If the SMC decides to switch from QD to BID dosing, there will be a figure for QD and a figure for BID dosing.

Additionally, the posterior probability of toxicity will be plotted versus the dose, using East.

